8.5.6. Vital Signs

Vital signs and change from baseline will be summarized descriptively at each visit by treatment group. Additionally, the number of subjects with the following vital signs of special interest will be summarized descriptively by treatment group:

[figure not shown]
- Systolic BP levels ≥180 mmHg
- Diastolic BP levels ≥100 mmHg
- Heart rate >180 beats/min
- Heart rate <60 beats/min

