All Participants will receive sixteen (16) 0.5-mL IM injections of Engensis or Placebo in each calf gastrocnemius muscle at each of two Visits during two Treatment Cycles: Treatment Cycle 1 on Day 0 and Day 14, and Treatment Cycle 2 on Day 90 and Day 104. At 2 hours ( $\pm$  1 hour) after completion of IM injections of Engensis or Placebo on Days 0 and 14 and Days 90 and 104, vital signs and blood draw for cytokine levels will be performed.

Treatment-emergent adverse event (TEAE) assessment, including injection site reactions, will start as of randomization (Day 0) and continue throughout the study.

Follow-up Study Visits will be conducted on Days 28, 60, 150, and 180 or early termination (ET). Vital signs will be recorded at all Study Visits. At the Day 180 Visit (end of study), the following assessments will be conducted: the full BPI-DPN (performed for 7 days prior to the Day 180 Visit), MNSI, BST, Patient Global Impression of Change (PGIC), and the quality of life assessments (36-item Short Form Health Survey [SF-36] and EuroQol Health Utilities Index [EQ-5D]), urine drug analysis, urine pregnancy status (females only), retinal funduscopy, physical examination, concomitant medications and procedures, and anti-HGF antibodies. Blood will be drawn for determination of serum chemistry, lipid profile, hematology, and HbA1c levels.

The purpose of this study is to assess the efficacy and safety of Engensis compared to Placebo as measured by changes in the means of the Average Daily Pain Scores (ADPSs) of the BPI-DPN, selected blood cytokines, BST, and assessments of injection site reactions, physical examination, laboratory assessments, vital signs, TEAEs, and treatment-emergent serious adverse events (TESAEs).

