### **5.2. Exclusion Criteria**

1. Other sources of pain that would prevent accurate assessment of DPN pain (e.g., thoracic and/or lumbar root proximal neuropathy, mononeuritis multiplex)

2. Peripheral neuropathy caused by a condition other than diabetes: e.g., anatomic (sciatic nerve compression), systemic (monoclonal gammopathy), metabolic (thyroid disease), and toxic (alcohol use) neuropathies
3. Has taken gabapentin or pregabalin during 30 days before completion of informed consent process or will take at any time during the study
4. Progressive or degenerative neurological disorder, such as amyotrophic lateral sclerosis (ALS), Alzheimer's disease, Parkinson's disease, vascular dementia, multiple sclerosis, or other neurological disorders determined by the Investigator to preclude participation
5. Symptomatic peripheral artery disease (PAD) or PAD requiring revascularization and/or that may interfere with the conduct of the study
6. Vasculitis, such as from Buerger's or other diseases
7. Systolic blood pressure >180 mm Hg on tolerable doses of standard antihypertensive medications at Screening determined by the Investigator to preclude participation
8. Hyperlipidemia or dyslipidemia not being treated with an optimal treatment regimen that follows the Standards of Care for hyperlipidemic/dyslipidemic patients with DM
9. Class 3 or 4 heart failure
10. Symptomatic bradycardia or untreated high degree atrioventricular block
11. Stroke or cerebrovascular accident or myocardial infarction within 3 months before Screening
12. eGFR < 30 mL/min/1.73 m^2 using the chronic kidney disease epidemiology collaboration (CKD-EPI) formula based on Cystatin C levels
13. Progressive renal dysfunction, defined as a decrease in eGFR to chronic kidney disease (CKD) Stage 1, 2, or 3 in the past 6 months before Screening
14. Ophthalmologic conditions pertinent to signs or symptoms of proliferative diabetic retinopathy (PDR) or other ocular conditions that preclude standard ophthalmologic examination
15. Myopathy (e.g., Duchenne or Becker muscular dystrophy, polymyositis)
16. Any prior or planned lower extremity amputation (excluding toe amputations) due to diabetic complications or prior lower leg injury (e.g., scarring, muscle atrophy) in the calf area (gastrocnemius) that would significantly reduce the surface area of the skin or amount of intact skeletal muscle required for the 16 treatment injections of Engensis

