#### **8.4.5. Vital Signs**

Vital signs will be measured at Screening, pre- and post-dose at Study Injection Visits during Treatment Cycle 1 (Days 0 and 14) and Treatment Cycle 2 (Days 90 and 104), and at all other Study Visits. Weight will be collected pre-dose at Study Injection Visits. After resting in the seated position for 5 minutes, vital signs measured will include temperature, sitting blood pressure, heart rate, respiratory rate, and oxygen saturation on room air. The method of temperature measurement should be according to the Site's policy and should be consistently applied.

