7.1. Baseline Definition

Unless specified otherwise, the baseline value for each variable is the value recorded at the last visit on or before start of dosing.

For the pain scores from the BPI-DPN eDiary, the baseline value is the Average Daily Pain Score prior to the Day 0 visit.

Note that, for eligibility, the mean of Average Daily Pain Scores of the BPI-DPN eDiary should be ≥ 4 during the 7 days prior to Day 0. For the Average Daily Pain Score calculation, at least five (5) days need to have the available scores.

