7.2. Visit Windows

Data at each scheduled follow-up visit will be analyzed according to the nominal visit identified on the data record.

In case of multiple different visits with the same nominal visit designation, the visit with the visit date closest to the target days of each protocol-specified visit schedule will be used for the efficacy analyses. For visits with the same distance to the target days, the later nominal visit record will be used. Data from all visits will be provided in the data listings.

If a subject fails to complete a study visit but provides necessary eDiary data during the time period expected for that visit (i.e. based on study day relative to the date of the first dose in VMDN-003-2), those eDiary data will be used to derive applicable endpoints. Day 90 endpoint would be derived by the eDiaries recorded 7 days up to 90 days from the date of first dose. Also, Day 104 endpoint would be derived by the eDiaries recorded 7 days up to 104 days from the date of first dose. Similarly, Day 180 endpoint would be derived by the eDiaries recorded 7 days up to 180 days from the date of first dose. Otherwise, if subject completes study visit, then date of visit will be used to derive applicable endpoints.

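### SAP 8.5.6 plans no same-day post-injection change in vital signs and does not split its threshold counts by baseline status, so the descriptive tables lose precision and specificity.

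*SAP*

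**What the plan says.** **Collection.** Protocol 8.4.5: "Vital signs will be measured at Screening, pre- and post-dose at Study Injection Visits during Treatment Cycle 1" (and likewise for Cycle 2). The Overall Design text in the synopsis sets the post-dose reading at 2 hours, give or take 1 hour, after the injections on Days 0, 14, 90 and 104, when "vital signs and blood draw for cytokine levels will be performed".

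**Analysis.** SAP 8.5.6: "Vital signs and change from baseline will be summarized descriptively at each visit by treatment group". It adds that "the number of subjects with the following vital signs of special interest will be summarized descriptively by treatment group", and lists systolic pressure ≥180 mmHg, diastolic pressure ≥100 mmHg, heart rate >180 and heart rate <60. The section does not mention that an injection visit yields two records.

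**Baseline.** SAP 7.1: "the baseline value for each variable is the value recorded at the last visit on or before start of dosing". For vital signs this is the pre-dose Day 0 value.

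**Repeat records.** SAP 7.2 resolves duplicate visits only by date and only for efficacy: "the visit with the visit date closest to the target days of each protocol-specified visit schedule will be used for the efficacy analyses". It does not choose between the pre-dose and post-dose readings of one visit.

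**Entry.** Protocol 5.2, criterion 7, excludes "Systolic blood pressure >180 mm Hg on tolerable doses of standard antihypertensive medications at Screening determined by the Investigator to preclude participation". Criterion 10 excludes bradycardia only when it is symptomatic. No diastolic limit is listed.

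**The concern.** Paired readings around an injection are most informative when one is subtracted from the other. The plan instead offers one change, from Day 0. A Day 14, 90 or 104 post-dose reading would then be set against a value nominally 14, 90 or 104 days older, although a pre-dose reading from the same day exists. Any acute effect of the repeat injections is added to whatever has changed since Day 0.

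The threshold counts have a similar weakness. As worded, a participant whose heart rate was below 60 at Screening counts the same as one who first fell below 60 two hours after an injection. A reader of the table could not tell the two apart.

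Safety is a stated secondary objective and is analysed descriptively only (SAP 4.4), so the table definitions carry most of the planned analysis of these readings.

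**Working it through.** The plan states no figure on this point, so there is none to reproduce. The check compares the texts and then sizes the loss with assumed inputs.

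**1. What the planned change contains.** For Days 14, 90 and 104:

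post-dose − Day 0 = (pre-dose that day − Day 0) + (post-dose − pre-dose that day)

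The second bracket is the acute change. SAP 8.5.6 plans at most the sum. On Day 0 the first bracket is zero, so change from baseline already is the acute change. The gap therefore concerns the other three injection days.

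**2. How the SAP treats comparable data.**
- Laboratory values (SAP 8.5.7): shift tables of baseline category against follow-up category.
- Injection-site events (SAP 8.5.2): pre- and post-injection assessments named for each of the four days.
- Vital signs (SAP 8.5.6): neither, although they share the pre/post schedule.

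**3. Precision of the systolic change.** From the SAP: 152 participants randomized 1:1, so 76 per arm. Assumed, because the documents give no vital-sign distributions: SD 14–18 mm Hg, correlation 0.4–0.6 with Day 0, and 0.75–0.85 with the same-day pre-dose reading.

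SD of change = SD × √(2(1 − r)); SE of arm difference = SD of change × √(2/76), where √(2/76) = 0.1622.

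| Reference | Smallest SE | Largest SE |
|---|---|---|
| Day 0 | 14 × √0.8 × 0.1622 = 2.0 | 18 × √1.2 × 0.1622 = 3.2 |
| Same-day pre-dose | 14 × √0.3 × 0.1622 = 1.2 | 18 × √0.5 × 0.1622 = 2.1 |

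The reduction does not depend on the SD:
- smallest: 1 − √(0.25/0.40) = 21%
- largest: 1 − √(0.15/0.60) = 50%

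If the correlation with Day 0 were as high as 0.7 and the same-day correlation only 0.75, the reduction would be 1 − √(0.25/0.30) = 9%.

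**4. Heart rate below 60.** The visit schedule gives 13 readings:
- 2 before the first injection: Screening and pre-dose Day 0
- 11 after it: post-dose Day 0; two each on Days 14, 90 and 104; one each on Days 28, 60, 150 and 180

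Assumed normal variation with mean 72, 76 or 80, between-person SD 8 or 10, and within-person SD 5 or 7, which makes 12 combinations, each simulated with 200,000 participants. Results across the 12:
- ever below 60: 8–49% of participants
- of those, already below 60 at Screening or pre-dose Day 0: 30–55%, which is about 4 to 37 people at N = 152
- combinations in which the prior-flag group is a majority: 1 of 12

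No corresponding estimate was made for the blood-pressure thresholds.

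**The case against.** **Other checks cover acute effects.** A reader might infer that the 2-hour reading is the only look at acute effects. It is not. Adverse events are assessed before and after dosing on all four days (Protocol Table 1). Injection sites are examined immediately, with a telephone call 2 to 3 days later, and cytokines are drawn at the same 2 hours. A vital-sign abnormality judged clinically significant, including worsening, is an adverse event (Protocol 10.2.1). All of this stands. These safeguards either measure something else or depend on investigator judgment, so they reduce the gap without closing it.

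**The arm comparison is protected.** A reader might infer bias. Placebo participants receive the same injections on the same days, so shared drift cancels between arms and pre-existing values balance in expectation. Only drift that differs by arm would blur the acute contrast.

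**The counts need not be mainly pre-existing.** That reading depends on the assumptions chosen. If 5–15% of an arm were permanently past a limit and 2–5% of the rest crossed it, the pre-existing share would run from 0.05/(0.05 + 0.95 × 0.05) = 51% to 0.15/(0.15 + 0.85 × 0.02) = 90%. Allowing for reading-to-reading variation, the heart-rate share is 30–55%. The documents cannot decide between these.

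**SAP 7.1 is adequate.** It speaks of a visit, and the Day 0 visit holds two readings. But a value taken 2 hours after the injections is not on or before the start of dosing, so the pre-dose value is the natural reading.

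**The text is silent rather than wrong.** SAP 8.5.6 does not say which reading represents an injection visit, and table shells might show both. Separate rows would let a reader approximate the mean same-day change, but not its SD or its outliers. If the post-dose reading were left out of the by-visit summary, the gap would be larger.

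**Conclusion.** The point holds as a gap in descriptive safety reporting. For Days 14, 90 and 104 no planned summary isolates the acute post-injection change. The four threshold counts can include values that predate treatment, and eligibility does not rule such values out. Sample size, type I error and the primary analysis are unaffected.

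The sizes, 21–50% on the systolic standard error and 30–55% on prior heart-rate flags, rest entirely on assumed SDs, correlations and heart-rate distributions. The first also compares two different changes, which share an expected arm difference only if pre-dose drift does not differ by arm. No test is planned, so the standard error here indicates how clearly a table would show an effect and is not a planned output. The documents do not support a claim of biased safety comparisons or of undetected acute harm.

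**What to change.** In SAP 8.5.6, before unblinding:

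1. For each injection day (0, 14, 90, 104), tabulate the pre-dose and 2-hour post-dose readings separately and add post-dose minus same-day pre-dose change. Keep change from Day 0, which answers the longer-term question.
2. Count threshold values on readings after the first injection. Report them by baseline status, new or already present, with denominators, and show worsening among those already past the limit. Put the 2-hour post-dose readings on their own line.

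Participants already past a limit should not simply be dropped from the counts, because a further rise or fall in them would then disappear from the table.

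Stating in SAP 7.1 that baseline is the last value before the first injection is an optional clarification.

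The cost is SAP wording, revised table shells and slightly longer safety tables. All readings are already collected.

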#### FOOTNOTES FOR SCHEDULE OF ACTIVITIES

\***Schedule of Activities** includes activities during Screening and all Study Visits. Additional data from daily eDiary entries will be transferred directly into a study database.

**Abbreviations:** D = Day; DPN = diabetic peripheral neuropathy; eDiary = electronic diary; ET = Early Termination; HbA1c = hemoglobin A1c; SF-36 = 36-Item Short Form Health Survey; EQ-5D = EuroQol Health Utilities Index

a The Day 14 Visit will be scheduled 13-15 days after the Day 0 Visit and the Day 104 Visit will be scheduled 13-15 days after the Day 90 Visit.

- Informed Consent** process is to be completed at Screening prior to conducting any study-specific procedures.
- Demographics and Baseline Characteristics** will include age, sex, race, and ethnicity collected at Screening.
- Medical History and Familial Cancer History:** A medical history and familial cancer history will be obtained at Screening, which will include a detailed assessment of past diabetes history, events, interventions, and procedures. Cancer history for 5 years will be collected at Screening.

4. **Vital Signs and Weight:** Vital signs will be measured at Screening, pre- and 2 hours ( $\pm$  1 hour) post-dose at Study Injection Visits during Treatment Cycle 1 (Days 0 and 14) and Treatment Cycle 2 (Days 90 and 104), and at all other Study Visits (Days 28, 60, 150, and 180 or Early Termination). After the Participant has rested in the seated position for 5 minutes, vital signs will be collected, including temperature, sitting blood pressure, heart rate, respiratory rate, and oxygen saturation on room air. The method of temperature measurement should be according to the Site's policy and should be consistently applied. Weight will be collected pre-dose at Study Injection Visits (Days 0, 14, 90, and 104).
5. **Height, Body Mass Index (BMI), and Waist Size** will be collected only at Screening.

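### The SAP's fast heart-rate row (above 180 beats/min on a seated, rested reading) will be empty or nearly so, so 0 versus 0 is not reassurance

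*SAP*

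**What the plan says.** SAP 8.5.6 has two parts. The first is a general summary: "Vital signs and change from baseline will be summarized descriptively at each visit by treatment group". The second is a set of threshold counts: "the number of subjects with the following vital signs of special interest will be summarized descriptively by treatment group". Four thresholds follow, two for blood pressure (one of them "Systolic BP levels ≥180 mmHg") and two for heart rate: "Heart rate >180 beats/min" and "Heart rate <60 beats/min". No reason is given for 180, and there is no lower fast-rate category. The text does not say whether pre-dose and post-dose readings are counted together, or whether a value already present before treatment counts.

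Protocol 8.4.5 fixes the measurement condition: "After resting in the seated position for 5 minutes, vital signs measured will include temperature, sitting blood pressure, heart rate". Footnote 4 of the Schedule of Activities repeats it: "After the Participant has rested in the seated position for 5 minutes, vital signs will be collected". Readings are taken at Screening, before and about 2 hours after dosing on Days 0, 14, 90 and 104, and at the other visits (Days 28, 60, 150 and 180).

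**The concern.** A threshold count is useful only if the threshold lies where the measurement can plausibly fall. A cut of 180 on a rested, seated reading appears far outside that range, while the slow cut of 60 lies close to ordinary resting values. The pair would then report slow rates freely and fast rates almost never.

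What is at stake is how one safety row is read. ECGs are scheduled only at Screening, pre-dose on Day 90 and on Day 180, and SAP 8.5.9 only lists them. The vital-sign reading is thus the only scheduled heart-rate measurement in the hours after an injection session. A row labelled as of special interest that shows zero in both arms invites the conclusion that injection did not raise heart rate. The row could not have shown otherwise for any rate up to and including 180.

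A second weakness is that the flags, as listed, are not tied to new occurrences. Exclusion criterion 10 removes only symptomatic bradycardia (and untreated high-degree block), so a participant may enter with a rate below 60 and be counted.

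**Working it through.** The documents derive no figure from this threshold, so there is no plan figure to reproduce. The check asks how many readings the flag can be expected to catch.

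**Inputs from the documents**
- Cuts: above 180 and below 60 beats/min (SAP 8.5.6).
- Participants: 152 to 250 (Protocol 5.3); 250 is used below because it gives the larger count.
- Post-baseline readings per participant: Day 0 post-dose (1), Days 14, 90 and 104 pre- and post-dose (6), Days 28, 60, 150 and 180 (4). Total 1 + 6 + 4 = 11, of which 4 are post-dose.

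**Inputs assumed**
- Resting heart rate roughly normal, mean 70 to 90, SD 10 to 20. The documents supply neither value.

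**Formulas**
- z = (180 − mean)/SD, and p = P(Z > z).
- Expected readings above 180 = 250 × 11 × p = 2,750 × p. This does not require readings within a participant to be independent.
- Slow flag: P(Z < (60 − mean)/SD).

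| Mean, SD | z for 180 | P(>180) per reading | Expected readings >180 in 2,750 | P(<60) | P(>100) | P(>120) |
|---|---|---|---|---|---|---|
| 70, 10 | 11.0 | 1.9e-28 | 5.3e-25 | 15.9% | 0.1% | <0.001% |
| 75, 12 | 8.8 | 1.1e-18 | 2.9e-15 | 10.6% | 1.9% | 0.009% |
| 80, 15 | 6.7 | 1.3e-11 | 3.6e-8 | 9.1% | 9.1% | 0.4% |
| 90, 15 | 6.0 | 9.9e-10 | 2.7e-6 | 2.3% | 25.2% | 2.3% |
| 90, 20 | 4.5 | 3.4e-6 | 0.0093 | 6.7% | 30.9% | 6.7% |

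In the least favourable row, 2,750 × 3.4e-6 ≈ 0.009. For the 1,000 post-dose readings alone (250 × 4) it is 0.0034. With 152 participants the figures are smaller.

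Two statements do not depend on the normal tail. First, from an assumed resting mean of 70 to 90, a rise of more than 90 to 110 beats/min (180 − 90 and 180 − 70) is needed before anything is counted. Second, for even one participant in 250 to be expected in this row, 1/250 = 0.4% of participants would need a scheduled seated reading above 180.

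**The case against.** The strongest reply is that the trial has other ways to see a fast heart rate. The by-visit summary in SAP 8.5.6 covers values and change from baseline, and under SAP 8.1 it includes the maximum and the 75th percentile. Protocol 10.2.1 makes clinically significant abnormal vital signs adverse events, and SAP 8.5.3 tabulates those by preferred term, severity and relationship. This stands. A reader might infer that the plan cannot show tachycardia after injection; the documents do not support that. What these routes do not give is the number of participants crossing a stated level. A maximum is a single value, and adverse event capture depends on investigator judgment. SAP 8.5.6 also does not say that its by-visit summary separates pre-dose from post-dose readings.

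Two further inferences should be resisted. That 180 was carried over from the systolic line is possible, but nothing in the documents confirms it. Nor do they state that the 2-hour readings are there to detect acute systemic reactions; they give only timing and content. The point needs neither.

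A third reply is that normal tails 4.5 to 11 SDs out are false precision. This also stands: the probabilities are orders of magnitude at best, and at that distance an arrhythmia, not ordinary variation, would fill the row. The eligibility criteria do not exclude tachyarrhythmias as such, so the count cannot be declared exactly zero. It remains uninformative about any lesser acceleration.

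A fourth reply is that a lower cut will flag benign readings. It will. At an assumed mean of 85 and SD of 14, P(>100) is 14.2%; over 12 readings treated as independent (a simplification), 1 − 0.858^12 ≈ 84% of participants would be flagged at least once. This supports a stricter second tier and a new-occurrence rule. It does not support keeping 180.

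Finally, an image between the lead sentence and the list in SAP 8.5.6 is missing from the copy reviewed, so a lost qualifier on timing or new occurrence cannot be ruled out. That part is best put as a request for clarification.

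**Conclusion.** The fast heart-rate row, followed as written, is uninformative. Across assumed resting means of 70 to 90 and SDs of 10 to 20, the expected number of flagged readings is at most about 0.01 in the largest planned trial, barring a rare extreme arrhythmia, while the slow flag fires on about 2% to 16% of readings. The conclusion rests on those assumed distributions, but it holds across the whole range and no reading of the text makes 180 a working cut. Zero in both arms should not be reported or read as evidence that heart rate was unaffected.

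The size of the problem is small. It is confined to one descriptive count. Safety analyses involve no formal testing, and no endpoint, stopping rule, alpha level or sample size in the documents uses the count. It is a minor safety-reporting correction, not a clinical-management rule.

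**What to change.** Before unblinding, amend SAP 8.5.6 as follows.
- Replace the above-180 reporting cut with a resting-range threshold, for example above 100 beats/min, with above 120 as a stricter tier. These values are illustrations and do not come from the documents; if the sponsor prefers another cut, or wishes to keep 180, the SAP should give the reason.
- Count the vital-sign flags only when they first occur after the first injection in a participant who did not meet them at the pre-dose Day 0 reading. This parallels the treatment-emergent restriction in SAP 8.5.3 and the baseline-to-follow-up shift tables in SAP 8.5.7.
- Show the 2-hour post-dose readings separately from the others.

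The cost is a changed number and a sentence or two in the SAP, plus a small programming change on data already collected. The table will contain some benign fast-rate counts, to be read as a comparison between arms.
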